Aim 1: Examine racial disparities in outcomes of PCSL patients with symptomatic GB disease with attention to conditional effects of social vulnerabilities. Hypothesis 1.1: Black patients are less likely to undergo cholecystectomy in the elective setting than White patients. Hypothesis 1.2: Time to consultation will modify the effect of race on elective cholecystectomy. Using PennMedicine data we will perform a retrospective cohort study of PCSL patients diagnosed with symptomatic GB disease between Jan. 1 2020 and Sept. 30, 2022. The primary independent variable will be race. Primary outcome will be cholecystectomy. Secondary outcomes will include time from referral to consultation and treatment, completion of consultation, urgency of operative treatment, and cost. Regression models with interaction terms will be used to evaluate effect modification of additional social vulnerability factors (e.g., ethnicity, primary language, insurance, income) on outcomes.

Aim 2: Comparative effectiveness study of telemedicine consultation for symptomatic GB disease in patients with social vulnerability (SV). Hypothesis 2.1: Recruitment will be feasible in the three-month pilot period. Hypothesis 2.2: Time to telemedicine consultation will be shorter than in-person consultation. We will perform a pilot study of telemedicine vs in-person surgical consultation for patients with SV with symptomatic GB disease seen in PCSL clinics between January and June 2023. Rates of surgical consultation will be compared between groups by consultation type. Secondary outcomes will be examined.

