Social vulnerability (SV) is a complex concept with many definitions that are situationally dependent. For this proposal, we define social vulnerability by race, ethnicity, primary language, insurance, and income, five components known to be associated with disparities in care for patients with SGBD. Preliminary data show that the majority of the Penn Medicine PCSL population with SGBD meet our criteria for SV (Black race, 21% (n=1978); Hispanic 6% (n=565); non-English primary language 4% (n=376); low-income neighborhood 91% (n=8573)). Further, in preliminary data, when examining differences across racial groups, for example, Black PCSL patients treated within the past 6 months at PennMedicine were more likely to undergo emergent (vs elective) cholecystectomy than White patients (Black: 65% (76/117); White: 41% (125/303); p<0.001). Emergent operations are associated with worse outcomes and greater costs.

Using data abstracted from PennChart, we will conduct an observational study of patients seen within the PCSL and the those discharged from the Emergency Department with symptomatic cholelithiasis and biliary colic between Jan. 1, 2020 and Sept. 30, 2022. These data will allow us to examine quality of care in two dimensions, safety and efficiency, for patients treated in the community setting. While we focus our analysis on race, we will study the conditional effects of other dimensions of SV on quality. **To date, the reasons for and impact of delays in treatment of symptomatic GB disease in Black patients and those with other SV within our PennMedicine community is unknown.** To test a solution to the problems of time off work and transportation, we will enroll patients with SV seen in the PCSL clinics in a pilot designed to test telemedicine as a mechanism to improve timely access to surgical care. Health equity will be measured by rates of surgical consultation among patients with SV and timeliness of surgical consultation and treatment.

RESEARCH PLAN AND METHODOLOGY

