Study Subjects and Eligibility Criteria Patients with a diagnosis of symptomatic cholelithiasis or biliary colic who were >18 years of age and enrolled in the Primary Care Service Line (PCSL) Registry in Clarity or evaluated and discharged from the Emergency Department (PAH, PPMC and HUP) between Jan. 1 2020 and Sept. 30, 2022 will be eligible for inclusion (data will be obtained for January 1 2020 to Dec. 31, 2022). The Primary Care Service Line (PCSL) covers more than 500,000 patients across the Penn Medicine catchment area including 12 contiguous urban, suburban, and rural counties in the tri-state area of PA, NJ, and DE (See Figure). The population is approximately 37.6% Black and 7.5% underinsured. Symptomatic cholelithiasis and biliary colic will be identified using International Classification of Diseases, Tenth Revision, Clinical Modification codes (ICD-10-CM). A 6-month “look-back” will be performed to confirm the first instance of disease. Patients with the following criteria will be excluded from study: 1) history of prior cholecystectomy 2) prisoners, or 3) contraindication to cholecystectomy including GB cancer, advanced cirrhosis and untreated coagulopathy.

Data Sources and Elements Clinical data will be abstracted from Clarity and financial data from the Horizon Performance Manager (HPM) dataset. This will allow real-world calculations of the value of care at Penn Medicine.

Definition of Social Vulnerability: Race will be the primary independent variable, given the established association between race and surgical disparities in the literature and preliminary data from Penn Chart. Ethnicity (Hispanic/non-Hispanic), primary language (English/non-English), insurance (Medicaid, Medicare, private, other) and low-income neighborhood (home zip code) will be identified in Clarity.

Covariates: Age, sex, comorbidities (defined by Elixhauser et al [28] using the index PCP visit and a 6-month look-back period), history of cholecystectomy, GB cancer, cirrhosis, coagulopathy and diagnostic imaging (US and CT SCAN) information will be obtained from Clarity. ICD-10 diagnosis codes will be used for clinical diagnoses. Date diagnosis add to chart, date of confirmatory imaging, date of discussion of treatment, date of referral to a surgeon and prisoner status will be obtained via direct chart review of PCSL notes within the 3-months following the initial diagnosis of SGBD. Access point will be designated as PCSL or Emergency Dept..

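### Aim 1 requires a 6-month look-back, but the stated data window opens on the first day of eligibility, so index dates from January to June 2020 cannot have a complete one

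*Combined protocol and SAP*

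**What the plan says.** The Aim 1 section of the protocol, under Study Subjects and Eligibility Criteria, takes patients enrolled in the primary care (PCSL) registry or "evaluated and discharged from the Emergency Department (PAH, PPMC and HUP) between Jan. 1 2020 and Sept. 30, 2022". The same sentence ends with a parenthesis giving the data period: "data will be obtained for January 1 2020 to Dec. 31, 2022". The cohort dates are repeated in the Aim 1 summary ("diagnosed with symptomatic GB disease between Jan. 1 2020 and Sept. 30, 2022") and under Equity Plan and Impact ("symptomatic cholelithiasis and biliary colic between Jan. 1, 2020 and Sept. 30, 2022"). Neither place gives an earlier start for the data.

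Two separate rules need records from before the index date:

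- **Incidence.** Under Study Subjects and Eligibility Criteria, a 6-month look-back "will be performed to confirm the first instance of disease".
- **Comorbidity.** Under Covariates, the Elixhauser conditions are defined "using the index PCP visit and a 6-month look-back period".

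Two other items under Covariates bear on the point. Some history items carry no date limit: "history of cholecystectomy, GB cancer, cirrhosis, coagulopathy and diagnostic imaging (US and CT SCAN) information will be obtained from Clarity". Certain dates, including when the diagnosis was added to the chart, come from "direct chart review of PCSL notes within the 3-months following the initial diagnosis of SGBD".

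**The concern.** The data window extends beyond the end of eligibility but not before its start. An analyst who extracts exactly the stated period cannot carry out the specified look-back for patients who enter in the first half of 2020.

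Two things are at stake in that segment:

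- **New versus prevalent disease.** A patient first diagnosed in late 2019 can be counted as a first instance in 2020. The 90-day cost window under Financial Outcomes would then start from a later encounter than the true first diagnosis.
- **Comorbidity adjustment.** The Analytic Strategy relies on multivariable regression to control confounding. Comorbidities would be captured over a shorter period for early entrants than for later ones in the same cohort.

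**Working it through.** The plan gives no figure of its own on this point. The check is calendar arithmetic.

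**Inputs**, all from the Aim 1 section:
- Eligibility: January 1, 2020 to September 30, 2022.
- Data window: January 1, 2020 to December 31, 2022.
- Look-back: 6 months before the index date. For the comorbidity rule, the index primary care visit is assumed to fall on the index date.
- Cost follow-up (Financial Outcomes): 90 days.

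**Step 1. Eligible dates.** 366 (2020) + 365 (2021) + 273 (January 1 to September 30, 2022) = 1,004.

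**Step 2. The two ends of the window.** After eligibility closes, October 1 to December 31, 2022 adds 92 days. September 30, 2022 plus 90 days is December 29, 2022, so cost follow-up is covered. Before eligibility opens, the window adds 0 days. The first index date needs July 1 to December 31, 2019, which is 184 days.

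**Step 3. Shortfall by index date.** Days needed = index date minus the date 6 calendar months earlier. Days available = index date minus January 1, 2020, capped at days needed. Shortfall = needed minus available.

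| Index date (2020) | Look-back starts | Needed | Available | Missing |
|---|---|---|---|---|
| January 1 | July 1, 2019 | 184 | 0 | 184 |
| March 31 | September 30, 2019 | 183 | 90 | 93 |
| June 30 | December 30, 2019 | 183 | 181 | 2 |
| July 1 | January 1, 2020 | 182 | 182 | 0 |

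**Step 4. Dates affected.** January 1 to June 30, 2020 is 31 + 29 + 31 + 30 + 31 + 30 = 182 dates.
- 182 / 1,004 = 18.1% have an incomplete look-back.
- 1,004 − 182 = 822 dates (81.9%) have a complete one.

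**Step 5. How uneven the shortfall is.** On April 1, 91 of 183 days are available, just under half (91.5). On April 2, 92 of 183 are, just over half.
- January 1 to April 1: 31 + 29 + 31 + 1 = 92 dates (92 / 1,004 = 9.2%) with less than half available.
- April 2 to June 30: 182 − 92 = 90 dates (9.0%) with at least half available.

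**Step 6. Sensitivity to the meaning of 6 months.** With a fixed 180 to 184 days, the last affected date moves between June 28 and July 2, 2020, and the share between 180 / 1,004 = 17.9% and 184 / 1,004 = 18.3%.

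**Step 7. Does the chart review close the gap?** Only in part. The 3-month limit governs which notes are read, not which dates they may report, so a 2019 diagnosis could be found. But the review covers primary care notes, while the cohort also admits discharges from three Emergency Departments. No rule excludes a patient on the date found, and the review does not supply the Elixhauser look-back.

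**The case against.** The strongest reply is that the parenthesis describes only the cohort and follow-up period, and that the look-back is a separate, more specific instruction. A look-back by definition reaches behind the index date, so a competent analyst would query 2019 records. The undated history items support this, since a history of gallbladder removal or cancer makes little sense if nothing before 2020 may be read. This reading is possible. The protocol does not state it, however: the parenthesis refers to data without qualification, and no section gives an extraction date before January 1, 2020. Even on this reading, the stated window is the text that needs correcting.

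Several narrower objections stand as limits on the point:

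- Comorbidities coded at the index visit are captured whatever the look-back, so the loss concerns only conditions recorded beforehand.
- The comorbidity look-back is anchored to a primary care visit, and the protocol defines no such visit for patients who enter through the Emergency Department. For them the day counts apply to the incidence rule, not necessarily to comorbidity.
- The shift in the cost window arises only if no 2019 records are queried, prevalent cases exist, and the charted diagnosis date is not used.
- Stratification by point of access is stated only under Financial Outcomes, so the uneven chart-review coverage bears on that planned analysis alone.
- The 18.1% is a share of dates, not of patients, and is not a measure of bias.

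None of these restores the missing look-back.

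**Conclusion.** The concern holds. A stated date conflicts with a stated rule in the same section. As written, 182 of 1,004 eligible dates (18.1%) have an incomplete look-back. The shortfall runs from the full 184 days on January 1, 2020 to 2 days on June 30, and from July 1, 2020 nothing is missing.

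This rests on taking the stated window literally and on a calendar 6-month look-back. It does not show that earlier records are unavailable. The number of patients affected, the amount of misclassification and any effect on the Black-White contrast cannot be determined from the documents. The matter should be fixed before extraction. Aim 2 is unaffected.

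**What to change.** Change the stated data window to start on July 1, 2019, and say that July to December 2019 is used for look-back only. Eligibility dates stay as they are. If an earlier look-back query is already intended, correct the window to show its start date.

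If 2019 data cannot be obtained, say so and report a sensitivity analysis that omits index dates from January to June 2020, leaving the 822 dates with a complete look-back.

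The cost is one date in a retrospective data request and one protocol sentence, or one extra model run in the fallback case.

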Scalability Preliminary data from Penn Chart shows that more than 9,400 PCSL patients seen within the last 6 months have a diagnosis of untreated symptomatic gallbladder disease, and less than 1000 have undergone appropriate treatment (see Figure). This proposal will use a robust approach to explain why patients in our community with symptomatic GB disease do not receive timely treatment (Aim1). Then, we will test the ability of telemedicine to improve timely access to surgical care (Aim2). Currently, PCSL and Emergency Medicine providers refer patients to in-person clinic visits with surgeons. These visits typically require at least a half day off from work, if not more. Since the onset of the pandemic, Penn Medicine surgical clinics have integrated telemedicine into routine practice. Telemedicine decreases time off from work and eliminates the need for transportation (two established barriers to surgical care) while promoting surgical health education, the establishment of trust, and ease of communication with the clinic. Patients will be randomized to a telemedicine preoperative surgical consultation or a traditional in-person surgical consultation. The Penn Medicine system has capacity for this volume of surgical referrals across the three downtown hospitals. Patients will be referred to the location that is most convenient for them. This proposal will pilot the use of telemedicine for patients with symptomatic gallbladder disease treated within the community practices of PennMedicine. We propose that, at scale, this initiative will encourage the **development of a Penn Pathway** for symptomatic cholelithiasis and biliary colic to improve patient and provider satisfaction and will show evidence of PennMedicine’s ability to eliminate unnecessary waste in the pathway to surgical health when negotiating **value-based purchasing agreements** with payers.

Equity Plan and Impact

GB disease, associated with obesity, is very common, especially among patients with social vulnerabilities [26, 27]. Guidelines recommend laparoscopic cholecystectomy, a safe and effective same day surgery, for patients with symptomatic cholelithiasis and biliary colic (SGBD). From the literature, we know that delays in care often result in emergent presentation which is significantly associated with increased rates of complications, prolonged hospitalization, and death.[8-10]

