Setting and Participants Patients ages 18+ years with symptomatic cholelithiasis or biliary colic who are a member of a racial or ethnic minority, not primary English speaking, from a low-income neighborhood or underinsured will be identified from the PCSL (see above) and Emergency Department (ED) discharges including referral to surgery. See **Figure** for exclusion criteria. After Institutional Review Board (IRB) approval, potential participants with a new ICD-10 code for symptomatic cholelithiasis or biliary colic seen by a PCSL provider between April 1, and June 30, 2023 will be identified. The diagnosis and discussion with the PCSL provider will be confirmed by chart review to ensure the patient is aware of their diagnosis. Then, patients will be recruited via the electronic health record. Nonresponses will be contacted by phone. If enrollment is lower than required, patients will be approached about participation at the time of the in-person PCSL or ED visit. Participation will be voluntary and informed consent will be obtained. For this pilot study, enrollment will proceed to a maximum of 25 per group. We anticipate between 2-37 eligible patients per week. Participants will receive an incentive of \$20 for participation. Demographics and clinical information will be collected in REDCap, a HIPPA-compliant, secure web application for building and managing online surveys and databases.

Exposure, Intervention Assignment, Covariates and Outcomes

Exposure: Assignment to telemedicine surgical consultation (vs. usual care) during the week of diagnosis of symptomatic cholelithiasis or biliary colic.

Intervention Assignment: Pragmatic randomization will be performed by group enrollment in alternating weeks.

Covariates: Participants will be followed for 6-months from enrollment. Data on patient attributes will include age, race, sex, insurance status, primary language and 9-digit zip code as a proxy for neighborhood income level. Clinical factors will be abstracted from the electronic medical record including comorbid conditions as defined in the Elixhauser Indices [28], bilirubin, liver function studies, ultrasound scan and CT scan results.

Outcomes: Primary outcome will be proportion of patients who undergo surgical consultation. Surgical consultation will be determined via chart review including care everywhere to

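### The 6-month look-back in Aim 1 is too short to establish first disease: long-untreated patients can enter as new cases with a misdated index, with an effect of unknown size and direction

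*Combined protocol and SAP*

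**What the plan says.** Study Subjects and Eligibility Criteria (Aim 1) identifies cases by ICD-10-CM code and states that a 6-month look-back "will be performed to confirm the first instance of disease". Cohort entry runs from 1 January 2020 to 30 September 2022. The data to be extracted also begin on 1 January 2020 and end on 31 December 2022.

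The Covariates paragraph of Aim 1 lists "Date diagnosis add to chart" among the items taken by chart review, together with the referral date. That review covers primary-care notes in the 3 months after the initial diagnosis. No rule says what happens when the chart date is older than the index code.

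Two other sections bear on how common old disease is:

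- Scalability reports that "more than 9,400 PCSL patients seen within the last 6 months have a diagnosis of untreated symptomatic gallbladder disease" and that "less than 1000 have undergone appropriate treatment".
- Setting and Participants (Aim 2) recruits "potential participants with a new ICD-10 code for symptomatic cholelithiasis or biliary colic" and adds: "We anticipate between 2-37 eligible patients per week".

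In the Aim 1 statement, cholecystectomy is the primary outcome, and the delay outcomes are measured from referral. Financial Outcomes counts costs over the 90 days after diagnosis.

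**The concern.** A look-back shows only that no code was recorded in the window searched. It establishes first disease only if patients with older disease are rarely uncoded for longer than that window. Here the plan itself describes a large group who carry the diagnosis and have not been treated. A patient from that group who goes more than 6 months without a relevant code and is then coded again passes the test and is counted as a first instance.

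Three parts of Aim 1 are exposed:

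- The 90-day cost window is tied to diagnosis, so it moves with a wrong index date.
- The referral date comes from notes written after the index, so an earlier referral can be missed and a later one taken as the start of the delay interval.
- Patients who have already remained untreated for a long time are mixed with newly diagnosed patients in the cholecystectomy comparison.

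If re-entry differs by race, the mixture differs between the groups being compared.

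**Working it through.** **Inputs from the documents.** Look-back 6 months (26 weeks). Pool more than 9,400; treated fewer than 1,000 (Scalability). Newly coded, Aim 2-eligible patients 2 to 37 a week (Setting and Participants). Subgroup counts 1,978 (21%), 565 (6%), 376 (4%) and 8,573 (91%) (Equity Plan and Impact). Cohort window 1 January 2020 to 30 September 2022.

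**1. Reproduce the pool.** Count divided by percentage: 1,978/0.21 = 9,419; 565/0.06 = 9,417; 376/0.04 = 9,400; 8,573/0.91 = 9,421. The figure reproduces. However, the Equity section applies these percentages to the whole primary-care population with symptomatic disease, whereas Scalability calls the 9,400 untreated. If about 9,421 is the total, at least 9,421 − 1,000 = 8,421 are untreated.

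**2. Stock against flow.** 26 × 2 = 52 and 26 × 37 = 962 newly coded patients per 6 months. 52/9,400 = 0.6%; 962/9,400 = 10.2%. Against 8,421 the upper figure is 962/8,421 = 11.4%. At face value, then, about 90% or more of the pool was diagnosed more than 6 months earlier.

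**3. How far the flow could be off.** For the whole pool to be new within 6 months, inflow would have to be 9,400/26 = 362 a week, 9.8 times the upper figure. For half to be new, 37 a week would have to be 962/4,700 = 20% of true inflow.

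**4. Cohort window.** 1,004 days = 143.4 weeks, giving 143.4 × 2 = 287 to 143.4 × 37 = 5,307 new cases.

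**5. Share of old cases in the cohort.** Older cases: 9,400 − 962 = 8,438. Let q be the fraction that re-enter once during the window after a gap of more than 6 months. The documents give no value, so q is assumed over a range. Share = 8,438q / (8,438q + new cases).

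| q (assumed) | re-entering | share at 37 a week | share at 2 a week |
|---|---|---|---|
| 1% | 84 | 2% | 23% |
| 5% | 422 | 7% | 60% |
| 10% | 844 | 14% | 75% |
| 25% | 2,110 | 28% | 88% |

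The same 8,438 is used in both columns. At 2 a week, 9,400 − 52 = 9,348 could be used instead, which moves the 1% and 25% rows of that column only to 25% and 89%.

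**6. Data window.** Index dates from 1 January to 30 June 2020 have no complete 6-month look-back within the stated extract: 182/1,004 = 18% of the entry period.

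**The case against.** The strongest reply is that stock and flow are not like with like. The 2 to 37 a week is eligibility for a 2023 pilot restricted to socially vulnerable patients, with exclusions given in a figure that is not reproduced. Aim 1 has no such restriction and covers other years. This stands as a limit on the exact percentages. It does not remove the contrast: 91% of the population is in low-income neighbourhoods, so the vulnerability criterion removes at most about 9%. The remaining exclusions, whose effect is unknown, would have to hide about four in five new cases before even half the pool could be recent.

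A second reply is that the chart-added date would expose older cases. It might, but it is read from primary-care notes after the index, may be unavailable for patients entering through the Emergency Department, and no rule acts on it.

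A reader might go further and infer that delay is understated. The documents do not support that. The delay interval starts at referral, so a late diagnosis date shortens it only where an earlier referral is missed. Re-entering patients are also those slow to be treated, which could lengthen mean delay.

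A reader might likewise infer that the Black-White comparison is biased. The preliminary racial difference concerns emergent versus elective surgery among operated patients. Nothing is reported on re-entry by race.

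Finally, applying 5% of 9,400 (470 patients) to a single 6-month period gives 470/(470 + 962) = 33% to 470/(470 + 52) = 90% old cases. That range varies only the inflow. Carrying it over the whole cohort needs the same re-entry every 6 months, although a patient can be a first instance only once.

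**Conclusion.** The point holds as a weakness in cohort definition. The only stated test of first disease is a 6-month code search. The plan's own figures make it probable that much of the untreated pool is older than that, and for the first 18% of the entry period the search cannot be completed in the stated extract.

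The share of misdated cases is not known. Under assumed re-entry of 1% to 25% it runs from about 2% to 28% at 37 new cases a week and from 23% to 88% at 2 a week. Both ranges rest on the Aim 2 rate standing in for Aim 1 incidence and on 9,400 being the untreated count. What is established is a risk of misdated index dates, which can shift the cost window, lose earlier referrals and mix long-untreated with new cases. The net effect on delay, on the cholecystectomy rate and on the racial contrast cannot be signed from the documents. The change is worth making because it is cheap, not because a particular bias has been shown.

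**What to change.** 1. Confirm the first instance against all of each patient's available Clarity history. This requires extending the extract to before 1 January 2020.
2. State a rule: when an earlier code, or the chart-added date already to be collected, precedes the index code by more than 6 months, the case is re-dated or analysed separately as prevalent. Simple exclusion would discard the long-untreated patients whose delays the study sets out to explain.
3. Keep the 6-month window for comorbidities.
4. Add a sensitivity analysis in patients with at least 24 months of prior record. Under the present extract this would be possible only for index dates from January 2022 (273/1,004 = 27% of the entry period), so it depends on step 1.
5. Say whether 9,400 is the untreated count or the total.

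The cost is a longer query, a somewhat smaller incident cohort, and history of unequal length between patients, which the sensitivity analysis addresses.
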